#### 4. Aims and Objectives

The overall aim of this research is to provide evidence on the extent, quality and safety of medical locum practice and the implications of medical locum working for health service organisation and delivery in primary and secondary care in the English NHS. Our three main research questions are:

**RQ1** – What is the nature, scale and scope of locum doctor working in the NHS in England? Why are locum doctors needed, what kinds of work do they undertake, and how is locum working organised? I RQ2 - How may locum doctor working arrangements affect patient safety and the quality of care? What are the mechanisms or factors which may lead to variations in safety /quality between locum and permanent doctors? What strategies or systems do organisations use to assure and improve safety and quality in locum practice? How do locum doctors themselves seek to assure and improve the quality and safety of their practice? I RQ3 – How do the clinical practice and performance of locum and permanent doctors compare? What differences in practice and performance exist and what consequences may they have for patient safety and quality of care?

This research is grounded in three main existing bodies of literature/theory which we have used to plan and frame our proposed empirical work: that related to temporary workers in organisations and the causes/consequences of precarious employment;(29-31) the wider literature on the sociology of the medical profession and particularly theories concerned with restratification and intraprofessional hierarchy and the nature and construction of professional identity; (32-34) and theories concerned with social identity and intergroup

relations, group identity and behaviours.(35, 36). The peripatetic nature of locum working may mean that locums practice on the periphery of healthcare organisations and of the profession, and may consequently have a weaker connection to organisational and professional norms and values. This raises questions about how locum doctors' professional autonomy and identity is constructed and legitimised relationally, how group identities and intergroup relationships are constructed and enacted, and the nature of intraprofessional group relationships and behaviours.

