#### **Primary care**

We will use the Clinical Practice Research Datalink (CPRD) to access electronic health records (EHRs) from primary care practices. The database holds anonymised general practice records on all registered patients, including diagnoses, test, prescribed treatments and referrals. Each interaction with a health professional is recorded, through unique identifiers for patients, consultations and health professionals. The staff role field can be used reliably to identify the type of GP (partner, salaried, or locum) involved in any recorded interaction. In addition, linkage to Hospital Episodes Statistics (HES) data is available. This allows us to obtain detailed information on any form of hospital attendance for all patients in the practices that are part of this linkage scheme. Our proposal plans to use data from both CPRD Gold (practices using Vision software) and the more recent CPRD Aurum (practices using EMIS). In total we should be able to access data from about 1,100 practices for a median period of 10 years, involving millions of patient, the great majority of which have given permission for the practice data to be linked to HES.

We will analyse the data in bins of financial years. Within each financial year, our population will comprise of patients registered with a CPRD general practice for whole of the year. Preliminary analyses in CPRD have confirmed that the available staff role identifier is widely and reliably used across practices, and we will use it to identify locum and permanent GPs. This will be our key parameter of interest and we will evaluate its association with important patient outcomes. All analyses will be conducted at the patient level.

We will focus on service utilisation and patient outcomes. Our primary outcomes will be patients revisiting the general practice within 7 days or 15 days. Secondary outcomes will include: referrals to secondary care, unplanned hospital admissions within 7 days or 15 days (through HES linkage), A&E attendance within 7 days or 15 days (through HES linkage), ambulatory care sensitive conditions (ACSC) hospitalisations within 7 days or 15 days (through HES linkage), antibiotic prescriptions, and validated prescribing safety indicators (as established measures of clinical performance and quality of care) which we have already used in a prior study using the CPRD.(44)

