All analyses will be controlled for available patient, general practitioner and general practice characteristics. Patient: age, sex, deprivation as measured by the 2015 Index of Multiple Deprivation (IMD, in quintiles),(45) years registered with the practice (if not collinear with age), number of practice visits in the previous financial year (or in the previous 12 months since the current consultation event) and numerous chronic conditions which are well recorded in these databases since they are part of the Quality and Outcomes Framework (atrial fibrillation, asthma, cancer, coronary heart disease, chronic kidney disease, chronic obstructive pulmonary disease, dementia, depression, diabetes, epilepsy, heart failure, hypertension, limiting disabilities, severe mental health, osteoporosis, peripheral arterial disease, rheumatoid arthritis and stroke).(46) General practitioner: sex/age are unavailable, but see analytical plan below). General practice: list-size, urban/rural location, practice location IMD (in quintiles), region, ratio of locum consultations over total within the

respective analysis year. We will also derive and describe consultation characteristics, like type, length and day of the week, although these will be used for descriptive purposes.

Our power calculation is based on the primary outcome, revisiting general practice within 7 days, and on the assumption that 10% of patients consulting a permanent GP return within that time period. Assuming 9 consultations with a permanent GP for 1 consultation with a locum, an alpha level of 5%, and an increase in the outcome to 15% for locum consultations (OR=1.59), we would need a total of 4330 patients to have 90% power to detect the association. Although this approach ignores between-practice variability in both the intercept and the association (e.g. varying return rates for permanent GPs and locus), it does demonstrate that we have many hundreds (if not thousands) times the numbers needed to detect a meaningful association.

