We will use two designs to reliably evaluate the association of interest. Within each financial year, we will randomly select one consultation for each patient, and then align all the outcomes and covariates to that specific event date for the patient. This will allow us to give equal weights to patients, and limit the potential for confounding introduced by patients with very poor health who may be visiting numerous times within a year. The first design, will involve a multi-level regression on all randomly selected consultation events, which will be used to obtain adjusted estimates for the exposure of interest. The second design will involve an additional step before the regression analysis, propensity score matching. This approach will attempt to select two patient samples for each exposure group (locum/permanent GP) that are as "close" and comparable as possible, in terms of all their available characteristics. We will use logistic regression to obtain the propensity score for each patient within a financial year, the probability of membership to each exposure group (locum/permanent GP) given the observed covariate values. The score will then be used to match patients in the two groups of interest, using their propensity scores (10 in the permanent GP group to 1 in the locum group – with no replacements). The propensity scores will be plotted over time and the performance of the matching process will be evaluated. Next, the matched sub-samples will be analysed with the multi-level regression models previously described. Our primary analyses will be the unmatched regressions, since our group has conducted methodological work that has demonstrated that matching can be detrimental in large samples (the methods work well for small and very small samples), while the recommended conditional regression approach for matched samples does not

confer any benefits (while it's less flexible when it comes to modelling the nested structure of the data).

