Data will be complete (e.g. a patient either is coded as having diabetes or not) and of high quality since tied to financial incentives (e.g. QOF) or almost impossible not to record (e.g. consultation, or prescribing). Therefore, we will not need to use a multiple imputation framework or anything similar. Confounding is a concern, with urgent requests perhaps being more likely handled by locums – e.g. a patient cannot afford to wait for 2 weeks before his/her regular GP is back from holiday. We will partly attempt to control for that through the available patient characteristics, but we will also interpret our results with caution and use the recently suggested E-Value to assess the potential effect of unmeasured confounding.(47) The age of GPs is not available in the database, and another concern is that locums may be much less experienced that permanent GPs, hence any potential differences could be attributed to that rather than the locum status. Although we need to be careful not to "overcontrol" the analyses for the characteristics of locum GPs, since numerous GPs close to or in retirement choose to locum, we will conduct a sensitivity analysis where we will exclude more experienced permanent GPs (thus focusing on GP registrars, salaried GPs and GP retainers vs locums, repeating all analyses previously described).

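### The secondary hospital outcomes in WP4 primary care do not separate consultation-day events from later ones, so the locum v permanent estimates cannot be read clearly as safety results

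*Protocol*

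**What the plan says.** Protocol section 5, WP4, Primary care, lists three secondary outcomes from linked HES data. Two are "unplanned hospital admissions within 7 days or 15 days (through HES linkage), A&E attendance within 7 days or 15 days (through HES linkage"). The third is "ambulatory care sensitive conditions (ACSC) hospitalisations within 7 days or 15 days (through HES linkage"). The start of each window is set by the design: one consultation per patient per financial year is drawn at random, and the team will "align all the outcomes and covariates to that specific event date for the patient". Binary outcomes then go into multi-level logistic models comparing locum with permanent GPs.

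No sentence excludes or separates events on the consultation day, or events that the consulting GP arranged. Escalation appears only as an outcome of its own: "Secondary outcomes will include: referrals to secondary care". That outcome is not described as emergency or same-day, and no rule connects it to the three hospital outcomes.

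Three other statements bear on interpretation. RQ3 (section 4, Aims and Objectives) asks "What differences in practice and performance exist and what consequences may they have for patient safety and quality of care". The confounding paragraph of WP4 mentions "urgent requests perhaps being more likely handled by locums". The covariate paragraph says the team will derive "consultation characteristics, like type, length and day of the week, although these will be used for descriptive purposes".

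**The concern.** An unplanned admission or A&E attendance can follow a consultation for two different reasons. On the day itself it may be the doctor's own action: acute illness was recognised and the patient was sent in. Some days later it more plausibly means that illness was missed or undertreated. For a question about safety these point in opposite directions, yet one yes/no variable records both alike.

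Two misreadings are then possible. A real locum excess of later events can look smaller than it is, because same-day events that do not differ between the groups are added to both sides. Alternatively, a locum excess can appear only because locums saw more urgent patients and escalated more of them on the day. The protocol concedes that urgency may differ, and the listed covariates (demographics, registration length, prior visits, chronic conditions, practice features) do not measure acuity at the consultation.

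**Working it through.** **Figures in the plan.** There is none to reproduce for the hospital outcomes. The only event rate given is for the primary outcome, practice revisit within 7 days: "10% of patients consulting a permanent GP return within that time period". It says nothing about hospital events, so the inputs below are assumptions shown over a range.

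**Step 1: reading the text.** The windows are 7 and 15 days, the anchor is the consultation date, and no day is excluded. On its natural reading day 0 is inside the window. This is an inference from those parts.

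**Step 2: formula.** Let
- *s* = share of permanent-GP window events that are same-day escalation (assumed 0.10 to 0.75);
- *E* = locum/permanent risk ratio for same-day escalation;
- *R* = locum/permanent risk ratio for later events.

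If each patient is counted in one component only, the risks add, and the combined risk ratio is

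RR = *s* × *E* + (1 − *s*) × *R*.

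Full cancellation (RR = 1) requires

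*E* = 1 − (1 − *s*)(*R* − 1)/*s*.

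**Step 3: dilution and cancellation.** Take *R* = 1.25. The middle columns use *E* = 1; the last column solves for cancellation.

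| *s* | Combined RR, *E* = 1 | Result | *E* needed for RR = 1 |
|---|---|---|---|
| 0.10 | 0.10 + 0.90 × 1.25 | 1.225 | impossible (−1.25) |
| 0.25 | 0.25 + 0.75 × 1.25 | 1.188 | 0.25 |
| 0.50 | 0.50 + 0.50 × 1.25 | 1.125 | 0.75 |
| 0.75 | 0.75 + 0.25 × 1.25 | 1.063 | 0.92 |

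With *R* = 1.50, cancellation is impossible at *s* = 0.25 (*E* = −0.50) and needs *E* = 0.50 at *s* = 0.50 or 0.83 at *s* = 0.75.

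**Step 4: the opposite error.** Suppose later events do not differ (*R* = 1), but locums escalate more on the day because they see more urgent patients, say *E* = 1.25. The combined RR is then *s* × 1.25 + (1 − *s*), which is 1.025, 1.063, 1.125 or 1.188 at the same four shares. The combined outcome shows a locum excess with no excess of later events. At *s* = 0.50 its value, 1.125, is the same as in Step 3, so the combined figure alone cannot tell the two situations apart.

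**Step 5: odds-ratio scale.** The planned models are logistic, but for uncommon events the conclusion is the same. With assumed permanent-GP risks of 0.5% same-day and 0.5% later, *R* = 1.25 and *E* = 1, the combined OR is (0.01125/0.98875)/(0.010/0.990) = 1.126, against a combined RR of 1.125.

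**Step 6: sample size.** The protocol says its data far exceed the 4330 patients required for the primary outcome. A larger sample narrows the interval around the combined ratio but does not separate its components.

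**The case against.** - **Day 0 is not stated to count.** True. The anchor is fixed, but the first day of counting is not put in words, and an analysis plan that is not shown may start at day 1. If so, what remains of the point is to report day 0 in its own right.
- **These are utilisation measures.** The protocol introduces the set as covering service use as well as patient outcomes, and never says that more admissions mean worse care. Total unplanned hospital use is a legitimate quantity whoever initiated it. This stands and is a reason to keep the combined version. It does not help a reader who takes that version to RQ3's safety question.
- **They are secondary, and referrals are reported separately.** Both true. The primary outcome, practice revisit, is untouched. Two outcomes sharing events is no error. Referrals give some context on escalation but do not remove GP-arranged events from the hospital outcomes.
- **Urgency is confounding, which the protocol already acknowledges.** It plans covariate adjustment, cautious interpretation and an E-value. Splitting the window does not remove that confounding either. The E-value, however, addresses unmeasured confounding and not an outcome that mixes two kinds of event.
- **A day-1 start is imperfect.** It moves patients who were sent home and returned the same evening out of the later window, keeps admissions that the GP arranged for the next day, and can favour a group that refers heavily on day 0, because fewer of its patients remain to be admitted. This stands, and it argues for showing the components side by side.

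A reader might also infer that real safety differences will cancel out. Figures can be built to show it: of 10,000 consultations in each group 100 need admission; one group sends 90 the same day and misses 10, the other sends 60 and misses 40. The combined risk is 1.00% in both (OR 1.0), while later events are 0.10% v 0.40%, OR (0.004/0.996)/(0.001/0.999) = 4.01. The arithmetic is right, but the inputs were chosen to cancel and the documents supply none of them.

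**Conclusion.** The point holds in a limited form. As worded, the three hospital outcomes do not distinguish consultation-day events from later ones, so the combined locum v permanent estimate has no clear safety meaning. Dilution follows at any nonzero same-day share if escalation is equal: from an assumed 1.25 to between about 1.23 and 1.06 over shares of 10% to 75%. A spurious excess is equally possible if urgent case mix differs. Full cancellation needs a substantial same-day share and a sizeable opposite difference in escalation, and should not be presented as the expected result.

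The conclusion rests on the natural reading that day 0 counts, on the premise that many same-day events are GP-arranged, and on assumed shares and ratios; the true size is unknown. The documents do not support saying that the plan labels correct escalation as harm. This is a worthwhile low-cost improvement to secondary outcomes, not a defect in the primary analysis.

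**What to change.** For unplanned admission, A&E attendance and ACSC hospitalisation alike:

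1. State in words on which day the window starts.
2. Prespecify and report day 0 separately, as a process measure of same-day escalation shown beside referrals.
3. Report days 1-7 and days 1-15, and base safety interpretation mainly on these. State how patients who already had a day-0 event are handled.
4. Keep the combined day 0-7 and day 0-15 versions as total-utilisation results.

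**Cost.** Some wording and a derived variable from dates already in the linked HES data. There are fewer events per component, which matters little at the sample size the protocol describes. Some same-day returns after a miss will fall in the day-0 category, and some GP-arranged admissions on day 1 will remain in the later window; the report should say so. Fixing the split before results are seen avoids a choice of window after the fact.

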All outcomes and key covariates of interest will be appropriately described over time, at the patient, GP and general practice level. For example, we will plot the percentage of revisits within 7 days by locum/permanent GP groups, across all practices, over time. We will use multi-level mixed effects logistic regression models to quantify the association between the exposure of interest (locum/permanent GP) and the outcomes of interest, controlling for all available covariates previously discussed. If an outcome (e.g. safety indicators) in better expressed as a count, e.g. if we identify that numerous indicators tend to apply to visits, we will use multi-level mixed effects Poisson or negative binomial regression models instead. Analyses will be conducted at the patient level, accounting for the nested structure of the data: patients within general practices, within regions. We will include random effects for practices and possibly for regions (alternatively a fixed effect for regions).

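### The WP4 primary-care models for HES-linked secondary outcomes adjust for prior practice visits but not prior hospital use, so residual differences in admission risk may remain in those locum estimates

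*Protocol*

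**What the plan says.** All of this is in the Protocol, section 5, WP4, Primary care.

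Three secondary outcomes come from HES: "unplanned hospital admissions within 7 days or 15 days (through HES linkage"), "A&E attendance within 7 days or 15 days (through HES linkage") and "ambulatory care sensitive conditions (ACSC) hospitalisations within 7 days or 15 days (through HES linkage"). The linkage is described as giving "detailed information on any form of hospital attendance for all patients in the practices" that take part in the scheme.

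On adjustment the plan states: "All analyses will be controlled for available patient, general practitioner and general practice characteristics". An itemised list follows. For patients it names age, sex, IMD quintile, years registered, 18 chronic conditions and one measure of earlier use of care: "number of practice visits in the previous financial year (or in the previous 12 months since the current consultation event"). Practice characteristics are listed after that. The modelling paragraph applies the same set to every outcome, "controlling for all available covariates previously discussed". The propensity score is also built from the observed covariates. No earlier admission, A&E attendance or ACSC admission appears in the list.

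The paragraph on confounding gives urgent requests as its example. It claims only partial control through patient characteristics, and adds cautious interpretation and the E-value.

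**The concern.** The plan treats its outcomes unevenly. For GP revisits it adjusts for how often the patient used the practice before. For hospital outcomes it does not adjust for how often the patient used the hospital before, although that history sits in the source that supplies the outcomes.

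The covariates that are listed are indirect substitutes. A condition flag says that a disease is present, not how severe or unstable it is. Practice visits are a different behaviour from emergency hospital use. If patients seen by locums and by permanent GPs still differ in prior hospital use after the listed covariates, part of that difference will appear as a locum association.

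Research question 3 asks about consequences for patient safety, and these outcomes bear on it directly. With the very large samples the plan expects, precision offers no protection against a small bias.

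**Working it through.** **1. The plan's own figure.** The only design figure is 4330 patients for GP revisit within 7 days (10% v 15%, 9:1, alpha 5%, power 90%). The odds ratio is (0.15/0.85)/(0.10/0.90) = 1.588, as stated. A two-sided Wald formula on the log odds ratio gives

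N = (1.960 + 1.282)² × [1/(0.1×0.15×0.85) + 1/(0.9×0.10×0.90)] / (ln 1.588)² = 4457,

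which is 2.9% above 4330. The usual pooled two-sided formula gives 4920. The point here depends on neither, because the figure concerns the primary outcome and does not change with the fix.

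**2. Text check.** Setting the outcome list beside the covariate list:

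| Outcome | Source | Prior use of the same service adjusted for? |
|---|---|---|
| GP revisit (primary) | CPRD | Yes, prior practice visits |
| Unplanned admission | HES | No |
| A&E attendance | HES | No |
| ACSC hospitalisation | HES | No |

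Only linked practices can supply the last three outcomes, and the same linkage covers those patients' earlier attendances. Coverage is therefore no obstacle.

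**3. Possible size, on assumptions only.** The protocol gives no prevalence of prior admission, no imbalance and no strength of association. Assume a binary marker of prior admission, with prevalence p in each group and risk ratio RR for the outcome, both taken as what remains after the listed covariates. Under a true null the expected risk ratio is

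(1 + (RR−1)·p_locum) / (1 + (RR−1)·p_perm).

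| p locum v permanent | RR 2 | RR 3 | RR 4 |
|---|---|---|---|
| 6% v 8% | 0.981 | 0.966 | 0.952 |
| 7% v 8% | 0.991 | 0.983 | 0.976 |
| 8% v 8% | 1.000 | 1.000 | 1.000 |
| 9% v 8% | 1.009 | 1.017 | 1.024 |
| 10% v 8% | 1.019 | 1.034 | 1.048 |

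The distortion is 0-5% and can go either way. More extreme inputs give more: 5% v 10% with RR 5 gives (1 + 4×0.10)/(1 + 4×0.05) = 1.40/1.20 = 1.17.

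**4. Against sampling error.** Assume N = 1,000 × 4330 = 4.33 million, split 9:1, and an event rate r of 0.5% or 1%. Then

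SE(log OR) = √[1/(0.1·N·r(1−r)) + 1/(0.9·N·r(1−r))] = 0.0227 at 0.5% and 0.0161 at 1%.

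The four unequal prevalence pairs, three risk ratios and two SEs make 24 combinations. Six exceed 1.96 SE:

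- RR 4 with a 2-point gap, in either direction and at either event rate (four combinations). For example, |ln 0.952|/0.0227 is about 2.2, and over 0.0161 about 3.1.
- RR 3 with a 2-point gap at the 1% event rate (two combinations, about 2.1 and 2.2 SE).

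The formula ignores clustering, which would normally widen the SE and reduce that count.

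**The case against.** **The list is not closed.** The plan speaks of available characteristics, and outcome-specific covariates are often left to an SAP, which was not examined here. But the protocol itemises the list, and the model paragraph refers back to what was already discussed. As written, prior hospital use is not in the models. Nothing forbids adding it, which is why this is an improvement to make and not a contradiction in the plan.

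**The listed covariates already work.** Age, sex, deprivation, years registered, practice visits and 18 conditions remove part of the admission risk. This stands. Only an imbalance that remains after them can bias the estimate, and the protocol holds no evidence that one exists.

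**One random consultation per patient per year limits the weight of very ill, frequent attenders.** True, but it equalises weights across patients. It does not balance illness between those seen by locums and those seen by permanent GPs.

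**The E-value guards against over-reading.** In part it does: a risk ratio of 1.05 has an E-value of 1.05 + √(1.05×0.05) = 1.28, which would be read as fragile. But the E-value is for unmeasured confounding and does not replace adjusting for a variable that is in hand.

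**Prior admissions do not measure how urgent today's consultation is.** This also stands. Urgency is the mechanism the protocol names, and the fix does not resolve it.

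**Conclusion.** The gap is real and specific: a baseline value that the linkage can supply is left out of the models for three secondary outcomes. Residual differences in admission risk may remain in those locum estimates. Size and direction cannot be derived from the protocol. The 0-5% illustration rests wholly on assumed prevalences and risk ratios, treated as conditional on the listed covariates.

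A reader might infer more, and the protocol does not support it:

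- That baseline differences in admission risk pass whole into the locum effect. They do not, because the listed covariates take out part of them.
- That a spurious significant result is to be expected. Only 6 of the 24 assumed combinations exceed 1.96 SE, before clustering.
- That the primary outcome shares the problem. It does not, because prior use of that service is already adjusted for.

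**What to change.** For the HES-linked outcomes only, add to the regression the patient's unplanned admissions and A&E attendances in the 12 months before the index consultation and, for the ACSC outcome, ACSC admissions in the same window. Counts grouped as 0, 1 and 2 or more would serve. The plan already contemplates a 12-month look-back for practice visits, so the construction is the same. Because the window closes before the index consultation, these covariates cannot lie on the path from that consultation to the outcome.

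For the matched analysis, which is not the primary one, fit a separate propensity score in the linked patients that includes the same covariates. The plan now describes one score per patient and financial year, so this means an additional score and matched sample for the linked subset.

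The cost is a few derived covariates and that extra matching step. The 4330 does not change. Keep the E-value and the cautious interpretation, since confounding by urgency of the consultation remains.
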